SAFETY EVALUATIONS	
Patients will be evaluable for safety if they have received any partial or complete treatment infusion.
 
All AEs will be graded according to the NCI-CTCAE v.4.
 
Treatment delays, dose reduction requirements and reason for treatment discontinuation will be monitored throughout the study.
 
The safety profile of patients will be monitored throughout the treatment and up to 30 days after the last treatment infusion (end of treatment, EOT), or until the patient starts a new antitumor therapy or until the date of death, whichever occurs first.
 
Any treatment-related AEs will be followed until recovery to at least grade 1 or stabilization of symptoms, whichever occurs first.

	
An interim safety analysis will be performed by the IDMC after the recruitment of the first 40 patients in the PM01183 arm (Arm A) to assess if the addition of primary CSF prophylaxis might be necessary. Although febrile neutropenia did not occur in the first-in-human PM01183 single-agent study, according to pooled data available from all ongoing phase II studies at 7.0 mg flat dose (FD), it occurred in about 16% of patients. In this clinical trial, the expected percentage of febrile neutropenia is lower, as the PM01183 dose will be administered based on BSA and with a dose (3.2 mg/m²) below the RD found in the first-in-human PM01183 trial (4.0 mg/m² = 7.0 mg FD).
 
Furthermore, PM01183, PLD and topotecan dose will be capped at a BSA of 2.0 m² in those patients who have a greater BSA.
 
At the time of the interim safety analysis, recruitment in the control arm (Arm B, PLD and topotecan) is also expected to be 40 patients.
 
Safety evaluations will be also performed by the IDMC during the futility analysis to be conducted in the two treatment arms once 210 patients are recruited (i.e., ~105 patients enrolled in each arm).
															
PATIENT-REPORTED OUTCOMES (PRO)	
PRO will be assessed every eight weeks from randomization and while on treatment to determine if efficacy and side effects are accompanied by measurable changes in the quality of life of patients. EORTC QLQ-C30 and EORTC QLQ-OV28 questionnaires will be used.
															

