Patient-reported outcomes (EORTC QLQ-C30 and EORTC QLQ-OV28 questionnaires)	-7 to 0 (+1 day)	Every eight weeks from randomization				•	-				

Assessments and procedures	Screening* (days before first drug infusion)	Treatment						End of treatment (EOT) †	Follow-up		
		Cycle 1		Cycle 2**		Further cycles**					
		D1	D8	D1	D8	D1	D8				
Concomitant therapies	-14 to 0	Throughout the "on-treatment period"***						-			
Adverse events	- §	Throughout the "on-treatment period"***						• (11)			

Regardless of the treatment administered, the same schedule of assessments will apply.

* Screening procedures will have to be repeated in case that the first infusion of the study treatment is given out of the established windows. **Note: Randomization of patients should occur as close in time as possible to the administration of the first dose of study drug.**

**Further treatment cycles will be administered every three weeks (\pm 48 hours) for PM01183 (Arm A) and topotecan (Arm B), or every four weeks (\pm 48 hours) for PLD (Arm B) if the patient fulfills all re-treatment criteria.

***"On treatment period" = from first infusion of the study treatment (PM01183, PLD or topotecan) to EOT [30 days after the day of the last dose administration, unless the patient starts a new antitumor therapy or dies (whichever occurs first), in which case the date of administration of this new therapy or the date of death will be considered the date of end of treatment].

† At 30 \pm 7 days after the last treatment infusion, an EOT should be performed. The listed assessments will have to be done if no recent data are available (i.e. within last 10 days prior to the EOT visit) or if the last data available show a grade \geq 2 treatment-related alteration whenever the medical condition of the patient may allow these evaluations.

§ Only information on SAEs that occur after signature of informed consent form is required. Grading should be as per NCI-CTCAE v. 4.

Time windows for Cycle 2 and further: a 3-day window will be allowed for laboratory tests and ECG, a 1-week window for tumor assessments as per RECIST v.1.1, tumor marker evaluation and patient-reported outcomes, a 1-day window for clinical assessments (ECOG PS, vital signs, weight, BSA, etc.), a 7-day window for the assessments at EOT, and a 2-week window for the follow-up period.

1. Height to be measured at baseline only.

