5.9 FOLLOW-UP AFTER END-OF-TREATMENT VISIT

Patients who finish treatment without radiological disease progression will be followed every eight weeks (\pm two weeks) from randomization until disease progression or start of a new antitumor therapy, death or until the date of study termination (clinical cutoff), whichever occurs first. Radiological tumor assessments and a tumor marker (CA-125) evaluation (if baseline levels were higher than normal) will be conducted during each of these follow-up visits. After radiological disease progression is documented or a new antitumor therapy is started, patients will be followed at least every three months (\pm two weeks) until death or date of study termination, whichever occurs first. Once the whole recruitment is completed, the 3-month follow-up for patients who discontinue treatment due to disease progression will be performed according to a calendar time. In this survival follow-up, for the purpose of collecting information, a documented telephone call would be acceptable.

The end-of-study date (clinical cutoff) is defined as 24 months after randomization of the last patient. The date and reason of the study discontinuation will be recorded on the patient's CRF (see Section [5.2.1.1](#)).

All AEs suspected to be related to the study treatment must be followed after the end of treatment until the event or its sequelae resolve or stabilize at a level acceptable to the Investigator.

Additional parameters and/or increased frequency of observations should be performed at the Investigator's discretion and according to the nature of the observed AEs. In case of death, autopsy data should be provided when available.

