7.6 PATIENT-REPORTED OUTCOMES

To measure the quality of life of patients, EORTC QLQ-C30 and EORTC QLQ-OV28 questionnaires will be analyzed every eight weeks from randomization and while on treatment.

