8.8 Decimal Places, Missing Values and Allowed Assessment Windows

By default, all results will be rounded to one decimal place, except when variables are integer, which will be reported without decimals (e.g., age in years, number of sites, etc.). For representing p-values four decimals will be selected as default but they could be rounded to fewer decimals if necessary.

Missing values will not be included in the calculation of outputs. Assessment windows as specified in the clinical protocol will be respected.

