12.8 PRO at treatment

Completion rate is defined as the number of patients with answer to item X in the numerator and the number of patients on treatment in each time point as denominator.

Missing data will not be taken into account in the analyses; anyway, if the quantity is considered relevant then supportive analyses will be performed applying a conservative approach of assuming missing data as failures.

Table 12.8.1 Completion rate

Item	Cycle	PM01183		Control	
		Missing (%)	Completed (%)	Missing (%)	Completed (%)
EORTC QLQ-C30					
Item 1	Baseline				
	Week 6				
	...				
....	Baseline				
	...				
Any item	Baseline				
	Week 6				
	...				
EORTC QLQ-OV28					
Item 31	Baseline				
	Week 6				
	...				
....	Baseline				
	...				
Any item	Baseline				
	Week 6				
	...				
EORTC QLQ-C30 and QLQ-OV28					
Any item	Baseline				
	...				

Table 12.8.2 T-test change vs. baseline

Item	Cycle	PM01183		Control*		p-value
		N	Mean (std)	N	Mean (std)	
*Control refers to PLD and/or topotecan						
Item 1	Week 6					
	Week 12					
	...					
....	Week 6					
	Week 12					
	...					
Item 58	Week 6					
	Week 12					
	...					
*Control refers to PLD						
Item 1	Week 6					
	Week 12					
	...					
....	Week 6					
	Week 12					
	...					
Item 58	Week 6					
	Week 12					
	...					
*Control refers to topotecan						
Item 1	Week 6					
	Week 12					
	...					
....	Week 6					
	Week 12					
	...					
Item 58	Week 6					
	Week 12					
	...					

Table 12.8.3 Percentage of patients with an improvement $\geq 10\%$ vs. baseline

Item	Cycle	PM01183		Control*		p-value
		N	%	N	%	
*Control refers to PLD and/or topotecan						
Item 1	Week 6					
	Week 12					
	...					
....	Week 6					
	Week 12					
	...					

[figure not shown]
Item	Cycle	PM01183		Control*		p-value
		N	%	N	%	
Item 58	Week 6					
	Week 12					
	...					
*Control refers to PLD						
Item 1	Week 6					
	Week 12					
	...					
....	Week 6					
	Week 12					
	...					
Item 58	Week 6					
	Week 12					
	...					
*Control refers to topotecan						
Item 1	Week 6					
	Week 12					
	...					
....	Week 6					
	Week 12					
	...					
Item 58	Week 6					
	Week 12					
	...					

Longitudinal analyses will be performed assuming a mixed-effect model with treatment (Y), time effect (days after baseline), and a time-treatment interaction as covariates, using a covariance structure of autoregressive order 1.

Table 12.8.4 Mixed effect model

Item	Estimated point change per day	p-value	Mean change during treatment

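### The by-visit quality-of-life tables use weeks that match no scheduled questionnaire and have no end-of-treatment row; separately, they are effectively observed-case, with completion counted only among patients on treatment.

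*SAP*

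**What the plan says.** **Collection.** The protocol synopsis states that "PRO will be assessed every eight weeks from randomization and while on treatment". Protocol 7.6 and SAP 8.4 give the same rhythm: "questionnaires will be analyzed every eight weeks from randomization and while on treatment". The notes to the Schedule of Assessments allow "a 1-week window for tumor assessments as per RECIST v.1.1, tumor marker evaluation and patient-reported outcomes", and SAP 8.8 adds: "Assessment windows as specified in the clinical protocol will be respected".

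Protocol 5.8 also requires both questionnaires at the EOT visit whatever the reason for stopping, unless a measurement exists from the preceding 10 days. The schedule shows none in follow-up. Patients who stop without progression still attend every eight weeks; under Protocol 5.9, imaging and (if raised at baseline) CA-125 "will be conducted during each of these follow-up visits".

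**Analysis.** SAP 12.8 defines the completion rate with "the number of patients on treatment in each time point as denominator". It continues: "Missing data will not be taken into account in the analyses". If the amount missing is judged relevant, a supportive analysis treats missing values as failures.

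Table 12.8.1 (completion) starts after baseline at Week 6. Table 12.8.2 (t-tests of change) and Table 12.8.3 ("Percentage of patients with an improvement" of at least 10%) are laid out at Week 6, Week 12 and onward. Table 12.8.4 is a mixed model with time in days.

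**The concern.** There are two separate problems.

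The first is a contradiction between the schedule and the table layouts. If the tables are programmed as drawn and the windows are respected, the named rows receive no scheduled questionnaire. The one record taken after a patient stops has no place in them.

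The second is what the by-visit comparisons condition on. Treatment stops for progression and toxicity, which are the events that quality of life is meant to reflect. When patients who have stopped leave the tables, an arm that loses its sickest patients sooner can look better among those who remain. Completion cannot reveal this, because its denominator shrinks with the patients lost.

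**Working it through.** **Visit grid.** Eight-weekly visits within 1 week cover weeks 7–9, 15–17, 23–25, 31–33, 39–41 and 47–49. The table grid, continued in steps of six, is 6, 12, 18, 24, 30, 36, 42 and 48. Only 24 and 48 fall in a window. The protocol's 2-week follow-up window does not rescue the layout: no questionnaire is due in follow-up, and even 2 weeks would leave week 12 unmatched.

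**Inputs for the dropout projection (SAP 5.2).** Control median PFS is 3.5 months, HR 0.7, exponential times, about 210 patients per arm. The PM01183 median is 3.5/0.7 = 5.0 months.

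**The plan's own figure.** Events = 4(1.960 + 1.282)²/(ln 0.7)² = 331, against 332 stated. Power with 332 events is 90.1%. The inputs are therefore those the plan used.

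**Share remaining.** S(t) = 0.5^(t/median), with 52.1775/12 = 4.348 weeks per month. Week 16 is 3.68 months and week 24 is 5.52 months. Protocol 5.2 keeps a patient on treatment until 30 days (4.29 weeks) after the last infusion, unless she dies or starts new therapy. The second version below allows for this by using t − 4.29 weeks.

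| | Control | PM01183 | Gap (points) |
|---|---|---|---|
| Week 16, progression-free | 48.3% (101 of 210) | 60.0% (126) | 11.7 |
| Week 16, with 30-day tail | 58.7% (123) | 68.8% (145) | 10.1 |
| Week 24, progression-free | 33.5% (70) | 46.5% (98) | 13.0 |
| Week 24, with 30-day tail | 40.7% (86) | 53.3% (112) | 12.6 |

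The tail version is the generous one. It adds 30 days after progression or death, whereas the protocol counts from the last infusion and ends the period at death or new therapy. Stops for toxicity or refusal would lower both versions, but the documents give no rate for them.

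**What completion would show.** If every patient on treatment answered at week 16, Table 12.8.1 would read 100% in both arms. Over all randomised patients the same data give 48% against 60%, or 59% against 69% with the tail.

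**Illustration for Table 12.8.3.** Suppose 15% of all randomised patients in each arm are improved at week 16, all of them still on treatment. The 15% is an assumed figure. An observed-case table would then show 0.15/0.587 = 26% against 0.15/0.688 = 22% with the tail, or 0.15/0.483 = 31% against 0.15/0.600 = 25% without it. Equal arms would appear to differ in favour of the one with more stopping.

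**The case against.** A reader might infer more than the documents support, and the sponsor could fairly object on several counts.

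- **That patients who stop leave no record.** They should give an EOT questionnaire, and they count as on treatment for up to 30 days. The gap is that the by-visit tables do not say where that record goes.
- **That the on-treatment denominator governs every table.** It defines completion only. Tables 12.8.2 and 12.8.3 state no denominator; that they are observed-case follows from leaving missing data out. Nor does the SAP define missing for the supportive analysis. Its only stated measure is Table 12.8.1, which does not count patients who have stopped.
- **That the week labels cause the loss of patients, or leave every row empty.** They remove nobody, and weeks 24 and 48 lie on both grids.
- **That the plan has no answer to dropout.** The mixed model uses days, keeps the earlier scores of patients who later stop, and ignores week labels. This stands, but the model relies on missing at random, which is doubtful when dropout follows progression or toxicity.
- **That on-treatment quality of life is the wrong question.** The synopsis states an on-treatment question, and no alpha or power is allotted to it. A responder rate over all randomised patients also absorbs PFS: if 30% of those remaining improve in each arm at week 16, it gives 14% against 18% (18% against 21% with the tail) purely because PFS differs. This is a good reason not to make that version the main one.

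**Conclusion.** The week grid and the missing EOT row are wrong as written and must be corrected.

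The dropout point holds as a limitation of the by-visit tables. They are effectively observed-case, and the supportive safeguard has no threshold, no definition of failure for a score, and a trigger that does not count patients who have stopped. On the plan's assumptions the share remaining differs between arms by 10 to 13 points at weeks 16 and 24, whether or not the 30-day tail is counted. These figures rest on exponential PFS standing in for time on treatment. The direction and size of any bias in the scores cannot be derived from the documents.

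The documents do not support concluding that the quality-of-life analysis as a whole is uninformative. The matter concerns a secondary endpoint, and the changes are worth making because they are cheap and alter what is reported.

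**What to change.** 1. Relabel Tables 12.8.1–12.8.3 to weeks 8, 16, 24 and so on (±1 week), add an EOT row, and say whether the EOT record enters the mixed model.
2. Report completion over all randomised patients (or those alive) beside the on-treatment rate, with reasons for missingness.
3. Keep the on-treatment version of Table 12.8.3 and state its denominator. Add a fixed, unconditional supportive version whose denominator is all randomised patients with a baseline score, counting those who stopped, progressed or died before the visit as not improved. Note in the text that this composite also reflects PFS.
4. Optionally, give both questionnaires at the existing eight-weekly follow-up visits of patients off treatment without progression.

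Items 1 to 3 are SAP text and table changes only. Item 4 needs a short protocol amendment and adds a small burden for patients; it does not cover those who stop for progression.

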Multivariate models (main effects or including interaction terms, if appropriate) will include all stratification factors and/or prognostic factors/covariates widely reported and recognized by the scientific community: treatment (PM01183 vs. control), ECOG PS (0 vs. ≥ 1 or coded as 0 vs. 1 vs. 2) prior platinum-free interval (1-3 months vs. >3 months or used as continuous variable), prior chemotherapy (1-2 vs. 3 lines or coded as 1 vs. 2 vs. 3), geographical area (USA vs. Europe vs. rest of the world), investigator's preference for the control arm (Topotecan vs. PLD), age, age at diagnosis, race (caucasian vs. other), histology type (serous/papillary vs. other), histology grade (poorly/undifferentiated vs. other), primary tumor site (ovarian vs. other), FIGO stage at diagnosis (metastatic/locally advanced [stage III] vs. other), FIGO stage at study entry (metastatic vs. locally advanced [stage III]/other), BRCA status (mutated vs. other), clinical/radiological signs of intestinal subocclusion at entry (yes vs. no), site of current disease: lung/liver (yes vs. no), liver metastases (yes vs. no), number of prior metastatic sites (≤ 2 vs. >2), body mass index (BMI), height, weight, body surface area (BSA), time from diagnosis to first infusion, prior cytoreduction (optimal vs. suboptimal vs. no surgery), prior radiotherapy (yes vs. no), platinum resistance (primary vs. secondary), clinically evidence of ascites at baseline (yes vs. no), time elapsed from last dose of last prior platinum-containing regimen to randomization, prior antiangiogenic treatment

with bevacizumab (yes vs. no), prior PARPi (yes vs. no), presence of any bulky (< 50 mm vs. \geq 50 mm) lesion at baseline, measurable disease (yes vs. no), sum of all target lesion diameters, baseline CA-125, albumin value at baseline, PFS prior line, response to last platinum therapy (yes vs. no) and baseline global QoL. In addition, continuous variables categorized as discrete variables will also be investigated in the continuum range and if the adjustment is better then the continuous variable will be selected in the model.

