8.4 Patient-reported Outcomes (PRO)

To measure the quality of life of patients, EORTC QLQ-C30 and EORTC QLQ-OV28 questionnaires will be analyzed every eight weeks from randomization and while on treatment.

PRO will be analyzed by means of longitudinal modelling and T-test comparisons to determine if efficacy and side effects are accompanied by measurable changes. The analysis will be performed on summary scores of EORTC QLQ-C30 and EORTC QLQ-OV28 questionnaires, as well as on subscales and individual symptoms.

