11.1.6 PRO Analyses

Table 11.1.6.1 PRO scores at baseline

Item	PM01183			Control								
				Total			PLD			Topotecan		
	N	Median (range)	Mean (std)	N	Median (range)	Mean (std)	N	Median (range)	Mean (std)	N	Median (range)	Mean (std)
EORTC QLQ-C30												
Item 1												
Item 2												
...												
Item 30												
EORTC QLQ-OV28												
Item 31												
...												
Item 58												

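### Visit-wise PRO comparisons use t-tests on change from baseline with no covariate, which is less precise than ANCOVA and over-corrects chance baseline imbalance

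*SAP*

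**What the plan says.** SAP 8.4 sets the method: "PRO will be analyzed by means of longitudinal modelling and T-test comparisons". The table shells in SAP 12.8 show what this means in practice.

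- The visit-wise comparison is "Table 12.8.2 T-test change vs. baseline", done item by item. It is run against the whole control arm and then against PLD and topotecan separately. No covariate is named.
- The longitudinal analysis is described as follows: "Longitudinal analyses will be performed assuming a mixed-effect model with treatment (Y), time effect (days after baseline), and a time-treatment interaction as covariates". No baseline score appears among the terms. The SAP does not say whether the response is the post-baseline score, the change score, or all scores with baseline as the day-0 value.

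Baseline scores are available. The protocol's Schedule of Assessments places both EORTC questionnaires at screening, and the SAP tabulates them by arm in "Table 11.1.6.1 PRO scores at baseline". The sponsor does treat baseline quality of life as prognostic elsewhere: the covariate list for the multivariate efficacy models in SAP 6.2 ends with "response to last platinum therapy (yes vs. no) and baseline global QoL". That list serves the Cox and logistic models, not the PRO analyses. Protocol 8.2.3 adds no adjustment.

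**The concern.** PRO is a named secondary endpoint. Questionnaires are collected while patients are on treatment, so fewer patients contribute at later visits and precision matters there. A change score fixes the coefficient of baseline at 1, whereas the regression of follow-up on baseline normally has a slope below 1. This has two consequences. The comparison is noisier than it needs to be. And an arm that by chance starts worse will tend to look as if it improved more, through regression to the mean alone. Estimating the coefficient, as ANCOVA does, removes both effects using data already in hand.

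**Working it through.** **The plan's own figure.** The documents give no PRO sample size, standard deviation, correlation or power, so there is no PRO figure to reproduce. The only sizing figure is 332 PFS events (SAP 5.2). It reproduces: the Schoenfeld formula with HR 0.70, one-sided 2.5% and 90% power gives 331 events, and 332 events give 90.1% power. It has no bearing on the PRO analyses.

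**Inputs.** Let s be the standard deviation at baseline and at follow-up (assumed equal), r their correlation (assumed, 0.3 to 0.8), and n the number per arm with both scores.

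**Precision of the visit-wise comparison.**
- Change score: Var = (2/n) × 2s²(1 − r).
- ANCOVA: Var = (2/n) × s²(1 − r²).
- Ratio: 2(1 − r)/[(1 − r)(1 + r)] = 2/(1 + r).

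The ratio does not depend on n. The power column takes an effect that ANCOVA detects with 80% power at two-sided 5%, and gives the power of the change-score t-test for that effect. The shift column is explained below.

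| r | Var(change)/Var(ANCOVA) | Power of t-test | Shift per unit of baseline difference |
|---|---|---|---|
| 0.3 | 1.54 | 62% | −0.7 |
| 0.5 | 1.33 | 68% | −0.5 |
| 0.7 | 1.18 | 73% | −0.3 |
| 0.8 | 1.11 | 76% | −0.2 |

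**If the variances differ.** With standard deviations s0 at baseline and s1 at follow-up, the per-patient variances are s0² + s1² − 2r·s0·s1 for change and s1²(1 − r²) for ANCOVA. Their difference is (s0 − r·s1)², which is never negative. So equal variances set the size of the loss but not its direction (in large samples, ignoring the one degree of freedom spent on the slope).

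**Imbalance.** Suppose there is no treatment effect and the arms differ by d at baseline. The expected follow-up difference is r·d, so the expected difference in change is r·d − d = (r − 1)d. With ANCOVA it is zero. With 210 per arm, the baseline difference has a standard deviation of s√(2/210) = 0.098s. An imbalance of 1.96 of these standard deviations shifts the change-score result by 1.96 × √((1 − r)/2) of its own standard errors: 1.16, 0.98, 0.76 and 0.62 for the four values of r.

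**Mixed model, if baseline is the day-0 response.** I compared the planned terms with a model that gives both arms one baseline mean. The calculation uses generalized least squares with linear time, equally spaced occasions, the SAP's autoregressive structure, and r as the correlation between adjacent occasions.

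| Occasions, including baseline | Variance ratio for slope difference, r = 0.5 | Same, r = 0.7 | Slope shift per occasion per unit of imbalance, r = 0.5 | Same, r = 0.7 |
|---|---|---|---|---|
| 2 | 1.33 | 1.18 | −0.50 | −0.30 |
| 3 | 1.63 | 1.35 | −0.38 | −0.26 |
| 4 | 1.87 | 1.50 | −0.29 | −0.22 |

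The shift is zero in the common-baseline model. With two occasions the variance ratio equals 2/(1 + r), as it should.

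**The case against.** A reader might infer that the mixed model leaves the baseline score out altogether. The documents do not support this. Time is counted in days from baseline, and Table 12.8.4 reports a change per day, which fits a model in which baseline is the first response. What stands is that the response vector is unstated and no common baseline mean is specified. On that favourable reading the free treatment main effect still costs precision and leaves an imbalance shift.

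A reader might also say that the t-test makes no adjustment for baseline. That is too strong: subtraction uses each patient's baseline and over-corrects for it.

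A third tempting criticism is that the covariance, "using a covariance structure of autoregressive order 1", clashes with time measured in days. Scheduled questionnaires are evenly spaced at eight weeks. The end-of-treatment questionnaire can fall off that grid, but protocol 5.8 requires it mainly when no recent one exists. The SAP does not say whether the structure runs by visit order or elapsed time, and no effect on any result has been shown. I do not press it.

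The strongest point on the other side is about importance. The PRO analyses have no stated hypothesis, alpha or power; they cover 58 items over many visits; and no decision rule rests on them. The loss also becomes small when r is about 0.8 or more. All of this is fair and limits the weight of the point. It does not make the change-score t-test the better choice, since ANCOVA uses the same patients and data.

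**Conclusion.** The point holds for the visit-wise comparison. The change-score t-test has a variance 11% to 54% above that of ANCOVA for r from 0.8 down to 0.3, and chance imbalance shifts its result by r − 1 per unit of baseline difference. These sizes rest on an assumed r and on equal variances; the direction does not depend on equal variances. For the mixed model the conclusion is narrower: the SAP does not define the response, and if baseline is the day-0 value the planned terms are less efficient than a common-baseline model.

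The limits are these. Against the whole control arm, under randomization and before dropout, the t-test is unbiased on average, so this is a matter of efficiency and conditional bias and not of an invalid analysis. The separate PLD and topotecan comparisons are a different case, because the control drug depends on prior therapy and investigator preference and SAP 12.8 states no matching restriction of the PM01183 arm. Baseline adjustment does not deal with informative dropout. The primary PFS analysis is not affected.

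**What to change.** In SAP 8.4 and Table 12.8.2, replace the t-tests with ANCOVA at each visit (treatment plus the baseline score of the same scale or item), or with baseline-adjusted visit contrasts from the longitudinal model.

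In SAP 12.8, state the mixed model's response vector and choose one of two forms:
- all scores including baseline, with the arms constrained to a common baseline mean, which keeps patients who have only a baseline questionnaire; or
- post-baseline scores with the baseline score as a covariate, which drops those patients.

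The cost is SAP wording and a model statement, with no new data or visits. Visit-wise ANCOVA loses no patients relative to the t-test, because a change score also needs both values. The choice should be fixed before the PRO data are analyzed.
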